**Relationship of Whole Blood Zinc Levels to Acne Severity Among Filipinos 18-25 years old: A
Cross-sectional Comparative Study in a Tertiary Government Hospital**

NCT04975412

Document date: Oct 25, 2017

Introduction:

Acne Vulgaris is a disorder of the pilosebaceous unit characterized by formation of comedones, papules, pustules, inflamed nodules, and cysts.¹ Most common predilection sites are those with hormonally sensitive sebaceous glands such as the face, neck, chest, upper back and upper arms.¹ Acne can persist for years and result in disfigurement and permanent scarring. It can cause serious adverse effects on psychosocial development, resulting in emotional problems, withdrawal from society, and depression.² Nearly all adolescents experience different severity levels of acne vulgaris, with moderate to severe levels affecting around 20% of this population.² In the Philippines, high school students were found to have a mild impairment of quality of life (QOL) due to acne, regardless of severity.³ Despite the known treatment regimens for acne, people are still suffering from the effects of the disease.

Acne has four main pathogenic contributors: follicular hyperkeratinization, increased sebum production, *Propionibacterium acnes* (*P. acnes*) within the follicle, and inflammation.^{1, 4} Reports show that antibiotic resistance is a growing issue in the treatment regimen of acne vulgaris, making it less and less suitable for long-term treatment.⁵ Other options that can be substitutes or adjuncts to treatment may be useful in this condition.

Zinc is an essential element for normal epithelial differentiation and for normal development. It has also been shown to have antioxidant properties.⁶ At present, there is paucity of data regarding the role of zinc levels in the development or severity of acne vulgaris. Also, data on favorable effects of dietary factors such as zinc, omega-3 fatty acids, antioxidants, vitamin A, and dietary fiber on acne vulgaris are limited specially in the Philippines.

This study will be conducted to measure the whole blood zinc levels in patients with acne vulgaris and compare it with healthy controls. This aims to determine the relationship between whole blood zinc levels and disease severity in Filipino patients with acne vulgaris in order to bring new insight to guide further studies regarding zinc's role in the pathogenesis and possible further treatment of acne vulgaris in the Philippines.

Review of Related Literature:

Acne Vulgaris is the eighth most prevalent disease in the world, affecting 9.4% of the global population.⁷ In adults, acne prevalence ranges from 50-54% in females and 40-42.5% in males.^{8,9} Acne is commonly misunderstood to affect primarily teenagers; however, a large proportion of individuals continue to suffer from acne or acquire new onset acne far after their adolescent years.⁸ Up to 64% of individuals have acne persisting into their 20s, and 43% have acne persisting into their 30s.² Moreover, the prevalence of acne did not substantially decrease until after the age of 44.⁹

Safe and effective long-term maintenance therapy is necessary in order to address the chronic and persistent nature of acne.⁵ In the last 3 decades, there has been a significant increase in resistance to antibiotics commonly used to treat acne. This was measured by the increased minimal inhibitory concentration (MIC) against *Propionibacterium acnes* for antibiotics such as erythromycin and tetracycline in patients receiving long-term antibiotic treatment. Increase in MIC was not found in acne patients who were not on antibiotic therapy and in non-acne patients.^{5, 10} This is a significant international public health concern because aside from increase in pathogenic *P. acnes*, resistance can occur in other bacteria more dangerous than *P. acnes*.

Given this situation and the complexity of the repercussions of this trend, it is a challenge to maximize the use of non-antimicrobial therapy when treating acne.^{5,11-14}

The development of a variety of skin disorders, including acne, has been linked to oxidative status. Oxidative stress can be measured using plasma levels of catalase (CAT), superoxide dismutase (SOD), total antioxidant capacity (TAC), and malondialdehyde (MDA). MDA, a marker for oxidative stress, was found to be higher in acne patients compared to controls. TAC together with the antioxidant enzymes, SOD and CAT, were lower for patients with acne. These results suggest that oxidative stress appears to play a major role in the pathogenesis of acne.¹⁵

Zinc is found in all body tissues. In skin, it is five to six times more abundant in the epidermis than in the dermis. Zinc is an essential element for cell health and proper bodily functions like glandular, reproductive, immune, and neuropsychiatric processes since the conformity, stability and activity of more than 200 metalloenzymes are affected by zinc. Its antioxidant properties have numerous benefits from protection against ultraviolet rays and oxidative damage by decreasing reactive oxygen species (ROS) to improvement of wound healing and prevention of cancer and cardiovascular disease.^{6,16}

Data suggest that zinc deficiency exist both in developed and developing countries, and several factors may affect the serum zinc levels, which include low intake of highly absorbable zinc in fresh foods, and high phytate content of some staple food, pregnancy, lactation, increased demands of physiological processes such as growth and sexual maturation.¹⁷ Whole blood zinc levels were measured from healthy subjects in relation to sex and age using atomic absorption spectrophotometry. Mean level of zinc obtained in whole human blood from males was 607.0 +/- 105.3 micrograms/100 ml and in females 585.2 +/- 122.9 micrograms/100 ml. The results showed that males had slightly higher zinc levels but the difference was not statistically significant.¹⁸ Zinc deficiency starts at 66 micrograms/dL for non-pregnant females and 70 micrograms/dL for males greater than 9 years old.¹⁹

The Agency for Toxic Substances and Disease Registry (ATSDR) states that inductively coupled plasma-atomic emission spectroscopy (ICP-AES) is used for zinc determinations in blood and tissue samples. This method is approved by the National Institute for Occupational Safety and Health (NIOSH). Samples are prepared by ashing or mineralization using acid digestion with nitric acid (HNO₃), perchloric acid (HClO₄), or sulfuric acid (H₂SO₄) in order to oxidize the organic sample and leave the inorganic component for analysis.²⁰ Atomic emission spectrometry (AES) is a technique commonly utilized for analyzing elements. This method records the electromagnetic radiation released by free atoms of the elements in the sample to be analyzed and uses the electromagnetic emission lines to determine the element. The prepared sample, once in the spectrometer, evaporates and atomizes in argon plasma flame, where temperatures can reach up to 10,000 K. The high temperature causes the excitation of atoms to higher electronic states. Atoms returning to the ground electron state emit electromagnetic radiation, which is measured by the spectrometer to determine the element.²¹

A few researches have been done in other countries comparing zinc levels in blood with the severity of acne. A study by Saleh done in Iraq measured trace elements in the blood, such as zinc and copper, and correlated it to the severity of acne vulgaris. The results showed that patients with severe acne had significantly lower levels of zinc.²² A study done in Iran suggested that zinc levels may be related to the severity and type of acne lesions in patients with acne vulgaris, with moderate and severe acne patients having lower serum zinc levels than mild acne

and control patients.²³ Another study of 173 acne patients published in the British Journal of Dermatology showed that retinol binding protein and serum zinc levels were significantly lower in severe acne.²⁴ The relative decrease of serum zinc levels in acne patients suggests a role for zinc in the pathogenesis of acne vulgaris. Studies about serum or whole blood zinc levels and acne severity in the Philippine setting have not yet been done.

The Global Acne Grading System (GAGS) is an acne severity scale that includes six locations on the face, chest and upper back. A factor is provided for each of the six locations based on size (forehead = 2, right cheek = 2, left cheek = 2, nose = 1, chin = 1, chest and upper back = 3). Each of the six areas are graded on a scale of 0-4 based on the most severe lesion present (no lesion = 0, comedones = 1, papules = 2, pustules = 3, nodules = 4). The local score per location is obtained by multiplying the factor with the corresponding score for the most severe lesion. The sum of the local scores from all locations will result to the global score, with zero as the lowest and 44 as the highest possible global score. Acne severity is rated as mild (1-18), moderate (19-30), severe (31-38), and very severe (≥ 39) with corresponding cut-off global scores.²⁵

Significance of the Study:

While a number of studies have been conducted comparing serum zinc levels with acne vulgaris, no previous studies have been done in the Philippine setting that assesses the relationship of whole blood zinc levels with the severity of acne. Given that acne vulgaris is one of the most common dermatologic diagnoses in the Philippine population, and the increasing resistance to antibiotics commonly used to treat acne, studies about other treatment modalities for acne vulgaris that do not have resistance factors are timely and significant in the country.

For long-term or maintenance therapy, physicians should consider effectiveness, cost, and adverse effects. By determining the relationship of whole blood zinc levels to acne severity among Filipinos 18-25 years old, this study can be used as evidence for giving zinc supplements to Filipino people diagnosed with acne vulgaris if a significant relationship is found. Since zinc is more cost-effective and has less adverse effects compared to most antibiotics, this may prove helpful for the Filipino patient in terms of safety and economy for long-term therapy. Furthermore, this study may also be able to provide more information for further studies towards non-antimicrobial treatment regimens for acne vulgaris in the Philippines.

Research Question:

Is there a relationship between whole blood zinc levels and the severity of acne vulgaris in Filipino patients 18-25 years old versus normal controls?

Objectives:

GENERAL

- To study the relationship between whole blood zinc levels and the severity of acne vulgaris in Filipino patients 18-25 years old and normal controls

SPECIFIC

- To describe the clinical profile of Filipino patients 18-25 years old with acne vulgaris

- To determine the whole blood zinc levels of acne patients compared to controls
- To determine the relationship of the clinical severity of acne vulgaris to whole blood zinc levels

Research Hypotheses:

Null Hypothesis: There is no relationship between whole blood zinc levels and the severity of acne vulgaris.

Alternative Hypothesis: There is a relationship between whole blood zinc levels and the severity of acne vulgaris.

METHODOLOGY

Study Design

A cross-sectional comparative study design will be utilized for this study which will be conducted from November 2017 to March 2018.

Study Setting

The study will be conducted at the Dermatology Out-patient Clinic of the East Avenue Medical Center (EAMC). The hospital has adequate staff and infrastructures to provide for the blood extraction of this study to be conducted properly. Laboratory services of Hi-Precision Diagnostics will be used for measuring whole blood zinc levels for this study.

Study Population

The participants of the study will include patients clinically diagnosed with acne vulgaris, aged 18-25 years of age.

Inclusion Criteria for Cases

- Filipino patients, aged 18-25 years old
- Diagnosis of Acne Vulgaris
- Able to read and write in English or Tagalog
- Seen at the Dermatology Out-Patient Department or Skin Center of East Avenue Medical Center

Exclusion Criteria for Cases

- Patients with other chronic dermatoses or systemic disease
- Taking oral supplements or medications for the past 3 months
- Patients who are pregnant or lactating

Inclusion Criteria for Controls

- Filipino patients, aged 18-25 years old
- Able to read and write in English or Tagalog
- Seen at the Dermatology Out-Patient Department or Skin Center of East Avenue Medical Center

[figure not shown]
Exclusion Criteria for Controls

- Patients with Acne Vulgaris or other chronic dermatoses or systemic disease
- Taking oral supplements or medications for the past 3 months
- Patients who are pregnant or lactating

Study Procedure

1. The study will be submitted to the Technical Review Board and Institution Ethics and Review Board for approval.
2. In the Dermatology Out-Patient Department of East Avenue Medical Center, patients seeking consult for their skin lesions which were diagnosed to be Acne Vulgaris will be screened if they meet the inclusion/exclusion criteria.
3. Informed consent will be obtained for those who are qualified.
4. Patients will be given proper treatment whether they agree to participate or not. For the patients who agree to participate, the investigator will assess the patient's acne severity using the Global Acne Grading Scale (GAGS).
5. Twelve milliliters of blood will be extracted from the patient with proper aseptic technique and waste disposal.
6. Blood sample will be properly stored in three EDTA tubes, labelled, and transported to the laboratory for determination of whole blood zinc levels through ashing acid digestion-inductively coupled plasma (ICP) using Shimadzu ICPS-7510, an inductively coupled plasma emission spectrometer.
 - a. Blood samples are viable and stable for 5 days at 15-25 degrees Celsius.
 - b. A memorandum of agreement between the principal investigator and Hi-Precision Diagnostics, Inc. has been made. Hi-Precision Diagnostics will be providing the materials for extraction, picking-up, and transporting the blood sample using a special insulated medical specimen bag (Versapak Pathology and Specimen bag) with ice packs and thermometer to help maintain the ideal temperature of 15-25 degrees Celsius.
 - c. Schedule of specimen pick-up is from 8:00 am- 8:00 pm and may be done on an as-needed basis. The blood specimens will be stored in the refrigerator immediately after extraction.
7. Results will be obtained by the investigator via the online results portal of the laboratory.
8. Data collected will be tabulated and data analysis will be done.

Study Framework/Process

Ethical Considerations

The protocol will be submitted for ethical review and approval by the Technical Review Board and Institutional Ethics and Review Board of the East Avenue Medical Center. Informed consent will be obtained from the participants prior to participation in the study. All data collection will be done in a setting that ensures patient safety and privacy. Patient will be assured of the confidential nature of the patient-provider interactions. Active listening, open-ended questions and clarifications will be used.

To ensure confidentiality in data collection, the investigators will assign a code to replace patient identifiers (e.g. name). Only authorized members of the research team will be allowed to access the result. The investigator will do physical examination of the patient to assess the severity classification, but no photographs will be taken of the patient or the skin lesions. No closed-circuit television or recording devices will be used in the rooms for interview and physical examination.

The Informed Consent Process

Informed consent will be obtained from the participants prior to participation in the study. At the onset, patient will be assured of the confidential nature of the patient-provider interaction. The investigator will explain that to ensure confidentiality in data collection, the investigators will assign a code to replace patient identifiers (e.g. name). Only authorized members of the research team will be allowed to access the result. All pertinent records will be stored in a locked cabinet. The records identifying the participant will be kept confidential and will not be made publicly available. In obtaining and documenting informed consent, the investigator adheres to Good Clinical Practice guidelines and to sound ethical principles. During the procurement of the informed consent, the investigator will go through the informed consent form which will include the following: that the patient will enter into a research study, the purpose of the study, the procedure to be followed, the possible risks involved (minimal chances of bleeding, bruising, infection, faintness or brief dizziness) and the expected benefits (patient will be able to know

his/her blood zinc levels). The participant will also be provided contact details of whom to speak to if she or he has any questions or any concerns regarding the study. The investigator will not coerce or unduly influence a patient to participate or to continue to participate in a trial without their consent. It will be emphasized that whether the patient chooses to participate or not participate in the study, he or she will still receive appropriate treatment. It will also be made clear that no compensation will be given for participating in the study. None of the oral and written information concerning the trial will contain any language that causes the participant to waive or to appear to waive any legal rights or that releases or appears to release the investigator for liability from negligence. Active listening, open-ended questions and clarifications will be used. The investigator will provide the participant with ample time and opportunity to inquire about details of the trial and to decide whether or not to participate in the trial. All questions will be answered to the satisfaction of the participant. By signing the consent form, the participant attests that the information in the consent form and any other written information was accurately explained and apparently understood by the participant and that informed consent was freely given. At any time during the process, the participant can opt to refuse from participating in the study.

STATISTICAL ANALYSIS PLAN

Justification of Sample Size:

PASS 2008 was used for the computation of minimum sample size. Parameters for the computation was obtained from previously published studies. For the one-way ANOVA, a minimum of 40 patients (10 for each acne severity: mild, moderate and severe acne and 10 for controls) achieves 95% power to detect differences among the means versus the alternative of equal means using an F test with a significance level of 0.05. The size of the variation in the means is represented by their standard deviation which is 13.30 mg/dL and the common standard deviation within a group is assumed to be 20.00 mg/dL.²²

Plan of Data Analysis:

Data will be encoded by the researcher in MS Excel. The excel file will be converted into Stata file for further data processing and analysis. Stata SE version 12 will be used for both descriptive and inferential statistics. Quantitative variables will be presented as mean or median while qualitative variables will be presented as percentages.

In order to compare the whole blood zinc levels between cases and controls, independent T-test will be used. ANOVA will be used to compare the whole blood zinc levels by acne severity. Multiple linear regression analysis will then be performed in order to determine the association of whole blood zinc levels with acne severity after controlling for the effects of significant confounding variables. All p values ≤ 0.05 will be considered as significant.

CONCLUSION

The correlation of whole blood zinc levels with severity of acne vulgaris in Filipino patients may help clinicians recommend more detailed dietary advice and add non-antibiotic supplements to their current treatment of acne vulgaris. The results of the study can serve as a guide for

further studies related to whole blood zinc and its role in the pathogenesis of acne vulgaris in Filipino patients.

Key Words: Whole Blood Zinc, Acne Vulgaris, Filipino

REFERENCES:

1. Aydemir EH. Acne vulgaris. *Turk Pediatri Ars*. Mar 2014;49(1):13-6. doi:10.5152/tpa.2014.1943
5. Humphrey S. Antibiotic resistance in acne treatment. *Skin Therapy Letter*. 2012;17(9):1-3.
6. Prasad AS. Zinc is an Antioxidant and Anti-Inflammatory Agent: Its Role in Human Health. *Frontiers in nutrition*. 2014;

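### The study can show only an association between zinc and acne, so a significant result is not evidence for supplementation, and the four-group F test alone does not show a relation with severity

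*Combined protocol and SAP*

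**What the plan says.** **Use of the result.** Significance of the Study says that "this study can be used as evidence for giving zinc supplements to Filipino people diagnosed with acne vulgaris if a significant relationship is found". The only condition is significance. The Conclusion is softer: it says the correlation may help clinicians with dietary advice and with adding non-antibiotic supplements, and that the results can guide further research. The Introduction is also modest: zinc is to be compared with severity "in order to bring new insight to guide further studies".

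**Design.** Under Study Design, "A cross-sectional comparative study design will be utilized". Study Procedure describes one GAGS grading and one blood collection. No zinc is given and no follow-up visit is described. Recent users of oral supplements are excluded.

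**Direction.** The Research Hypotheses are non-directional, and the Plan of Data Analysis treats any p value of 0.05 or less as significant. The Review of Related Literature does have a direction. Of one earlier study it says "The results showed that patients with severe acne had significantly lower levels of zinc"; another is reported as finding "moderate and severe acne patients having lower serum zinc levels than mild acne" and control patients. It also argues from lower serum zinc in acne patients generally.

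**Two questions.** The specific objectives separate "To determine the whole blood zinc levels of acne patients compared to controls" from "To determine the relationship of the clinical severity of acne vulgaris to whole blood zinc levels". The Research Question joins them: "Is there a relationship between whole blood zinc levels and the severity of acne vulgaris in Filipino patients 18-25 years old versus normal controls". The Plan of Data Analysis gives cases versus controls a t-test and severity an ANOVA, then a multiple linear regression. It does not say whether the ANOVA by severity includes controls. Justification of Sample Size does include them: 10 mild, 10 moderate, 10 severe and 10 controls.

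**The concern.** A single measurement of zinc and severity cannot show that low zinc came before the acne, nor that giving zinc would change it. The sample also carries no information on supplementation, because recent users are excluded and nobody receives zinc. Regression adjustment does not close this gap: it can reduce confounding by measured variables, but it does not turn an association into a treatment effect.

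Taken literally, the sentence would also be satisfied by higher zinc in worse acne, which would not support giving zinc.

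The severity claim has a further weakness. A four-group F test asks whether any of the four means differ. If controls alone stand apart, F will usually be significant although zinc does not vary with severity at all. A report that follows the joined research question could then present a case-control difference as a severity relationship.

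**Working it through.** The main point needs no arithmetic. The claimed use requires evidence on the effect of giving zinc, and Study Design and Study Procedure contain nothing that could supply it. The calculations below concern the severity point.

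**Inputs** (Justification of Sample Size): 4 groups of 10, N = 40; SD of the group means 13.30; within-group SD 20.00; alpha 0.05. The patterns of means below are assumptions, each scaled to an SD of means of 13.30.

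**1. The plan's own figure.**
- λ = N × (SD of means / within-group SD)² = 40 × (13.30/20)² = 17.69, with 3 and 36 degrees of freedom.
- Power from the noncentral F distribution is 93.2%, against 95% stated. At 11 per group it is 95.5%. The stated figure is reproduced to within 2 points.

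**2. F does not depend on the pattern.** λ depends on the means only through their SD, so power is 93.2% whether zinc falls with severity, rises with it, or differs in one group only. Inspecting the observed means does settle direction: in 200,000 simulated studies per pattern, a significant F with a negative observed four-group slope occurred in 93.1% under a falling pattern and 0.0% under a rising one.

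**3. Only controls differ, acne grades flat.**
- One group of four apart: SD of means = gap × √(3/16), so gap = 13.30/0.433 = 30.7.
- Four-group F significant: 93.2%.
- Planned t-test, 30 cases against 10 controls: noncentrality 30.7/(20 × √(1/30 + 1/10)) = 4.21; power 98.4%.
- ANOVA of the three acne grades alone: significant in 4.9%, which is the nominal error rate.
- Linear grade term among acne patients: significantly negative in 2.5%, again the nominal rate.

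So in this case F and the t-test both detect the case-control difference, and only a comparison within acne patients shows that there is no severity relation.

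**4. Power of a within-acne severity term, equally spaced means.**
- Step = 13.30/√1.25 = 11.90 per grade.
- Mild, moderate and severe scored −1, 0, +1 with 10 each: Sxx = 10 × (1 + 0 + 1) = 20; SE = 20/√20 = 4.47.
- Noncentrality = 11.90/4.47 = 2.66. Power is 72.8% with error from the 30 acne patients alone (df 28) and 73.5% with controls in the regression (df 37).
- Expected 95% CI half-width is about 9.1 per grade (df 37).

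**5. Sensitivity to the SD.** The Review of Related Literature quotes whole-blood SDs of 105.3 (males) and 122.9 (females) micrograms/100 ml. If those applied, with 13.30 read in the same unit (an assumption):
- λ = 40 × (13.30/105.3)² = 0.64 or 40 × (13.30/122.9)² = 0.47, and F has 8–9% power.
- The grade term has noncentrality 0.51 or 0.43 and power of 6–7%.

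That is a separate sample-size question, but it limits how far the 73% can be trusted.

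**The case against.** The strongest reply is that the sentence is rationale and governs no analysis. Being usable as evidence is less than proof, the same section speaks of informing further studies, and the Introduction and Conclusion are modest. This stands in part: no test, endpoint or sample size is wrong, and the Conclusion hardly needs changing. But the modest statements sit beside the supplement sentence without limiting it, and nowhere does the document say that the design shows association only.

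On direction, the reply is that the background makes the expected direction plain and the group means will show it. That largely stands. The omission is small and wording cures it.

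A reader might infer that the rationale holds only if zinc is lower in worse acne. The documents do not support this. The Review of Related Literature also argues from lower zinc in acne patients as a whole, and the supplement sentence concerns anyone diagnosed with acne. Lower zinc in all grades than in controls would fit that rationale; it would not be a severity relation.

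A reader might also infer that the plan merges the two questions throughout. It does not. The objectives are separate, cases versus controls has its own t-test, and no ordered slope with controls scored 0 is specified. What remains is narrower: the only severity ANOVA whose composition is stated includes controls, and a significant result from it does not by itself answer the severity objective.

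**Conclusion.** The concern holds as a limit on interpretation. A significant result would be a cross-sectional association. It would not show that supplementation improves acne, and the sentence in Significance of the Study goes further than the design allows. This conclusion rests on the design alone.

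The severity point also holds. With the plan's inputs, the four-group F is significant in about 93% of studies even when zinc is flat across acne grades and only controls differ. This assumes the stated SDs, equal groups of 10, and an analysis made up as the sample size section describes.

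It might be inferred that the hypotheses should be one-sided or the ANOVA replaced. Neither follows: two-sided testing is appropriate, and the F test has more power than a severity term for the overall comparison.

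**What to change.** **1. Reword the sentence in Significance of the Study**, for example: *A significant association with lower zinc in acne patients than in controls, or in worse acne, would be a cross-sectional finding that may justify an interventional study of zinc; it is not by itself evidence that supplementation improves acne.* The Conclusion needs at most a matching phrase.

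**2. Keep the t-test and the four-group ANOVA, and base the severity conclusion on a comparison within acne patients.** One way is a separate severity term in the planned regression, beside the term for acne versus control, each reported with a 95% CI. This takes zinc as the outcome, which the Plan of Data Analysis does not state and should. The term must cover every GAGS grade enrolled. The scale described in the Review of Related Literature has a very severe grade (39 or more) that no exclusion criterion removes, so a three-level score would leave such patients without a code. Using the GAGS score itself avoids this.

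**Cost.** One sentence, one regression term and its interval; no added patients, samples or visits. The claim becomes narrower. The severity term uses only the acne patients (30 as planned) and has less power than the four-group F: about 73% against 93% under equal spacing and an SD of 20, and far less if the quoted whole-blood SDs apply. It therefore supplements the ANOVA, and a non-significant severity term should be read from its interval, not as proof of no relation.

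### Does immediate refrigeration of specimens, when the plan states stability only at 15-25 °C, threaten the zinc comparison?

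*Combined protocol and SAP*

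**What the plan says.** All the relevant text is in the protocol's Study Procedure, step 6.

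- Step 6a: "Blood samples are viable and stable for 5 days at 15-25 degrees Celsius". This is the only stability statement in the document.
- Step 6b: the laboratory supplies an insulated bag for collecting and transporting specimens, "with ice packs and thermometer to help maintain the ideal temperature of 15-25 degrees Celsius". It also mentions a memorandum of agreement with the laboratory, which is not part of the document.
- Step 6c: "Schedule of specimen pick-up is from 8:00 am- 8:00 pm and may be done on an as-needed basis", followed by "The blood specimens will be stored in the refrigerator immediately after extraction". No refrigerator temperature or maximum holding time is given.

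The head of step 6 names the assay: ashing and acid digestion followed by inductively coupled plasma emission spectrometry. Whole blood zinc is the only laboratory measurement. Under Plan of Data Analysis it is compared between cases and controls by t-test, and "ANOVA will be used to compare the whole blood zinc levels by acne severity". A multiple linear regression follows.

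**The concern.** In its ordinary meaning a refrigerator is colder than 15 °C. Staff following step 6c would therefore hold every specimen, for some time, below the range that steps 6a and 6b call stable and ideal. Pick-up is on demand within a 12-hour window, so the time in the refrigerator would vary from one participant to the next.

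All the inferential analyses rest on the zinc value. If cold storage changed that value, and if cases and controls or the severity groups were held for different times, the storage effect would be mixed into the group comparison. The planning minimum is 10 per group, so a few specimens handled differently could matter. The protocol asks for no record of draw time, storage temperature or assay time, so the question could not be examined afterwards.

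**Working it through.** **1. Do the three sub-steps exclude one another?**

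| Sub-step | Stage | Kind of statement | Temperature |
|---|---|---|---|
| 6a | not limited to a stage | stability claim, 5 days | 15-25 °C |
| 6b | collection and transport | target for the bag | 15-25 °C |
| 6c | extraction to pick-up | instruction | refrigerator, no set point |

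Steps 6b and 6c can be followed in sequence: refrigerate until collection, then transport at 15-25 °C. Step 6a reports a condition under which samples keep. It does not say that they fail outside it. What is missing is a stability statement for the refrigerated stage.

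**2. How far outside the range?** The document gives no refrigerator temperature. If 2-8 °C is assumed, the shortfall below the lower limit is 15 − 8 = 7 °C to 15 − 2 = 13 °C. That measures a departure in temperature, not an error in zinc.

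**3. Is there a route from cooling to a wrong zinc value?** The analyte is an element. The Review of Related Literature explains that acid digestion oxidizes the organic part of the sample and leaves the inorganic part to be measured. The specimen is whole blood, so zinc that moved between cells and plasma would still be in the tube (assuming the tube is mixed before a portion is taken). Nothing in the document indicates that refrigeration changes total zinc.

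**4. What would group bias require?** To first order, bias in a group difference = (change in measured zinc per hour of storage) × (difference in mean storage hours between groups). It is zero if either factor is zero. The document gives a value for neither, and step 6c applies one instruction to the blood specimens without naming a group.

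**5. What would random handling error cost?** Inputs from Justification of Sample Size: 4 groups of 10, SD of the means 13.30, within-group SD 20.00 (units as printed), and a stated 95% power "using an F test with a significance level of 0.05".

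The plan's own figure first:

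- λ = N × (SD of means / within-group SD)² = 40 × (13.30/20.00)² = 17.69.
- The noncentral F distribution with 3 and 36 degrees of freedom at 0.05 gives power of 93.2%, within 2 points of the stated 95%.

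Now let handling add independent error with SD equal to r times the within-group SD. The total SD becomes 20.00 × √(1 + r²), and λ is divided by 1 + r². The values of r are assumed, because the document gives none.

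| r | Total SD | λ | Power |
|---|---|---|---|
| 0 | 20.00 | 17.69 | 93.2% |
| 0.10 | 20.10 | 17.51 | 92.9% |
| 0.25 | 20.62 | 16.65 | 91.5% |
| 0.50 | 22.36 | 14.15 | 86.2% |

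The loss is 0.3 points at r = 0.10, 1.7 at r = 0.25 and 7.0 at r = 0.50. Nothing in the document places handling error anywhere in this range. The table covers lost precision only; bias is dealt with in item 4.

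**The case for a change.** The strongest case for a change is that step 6a is not confined to transport. A 5-day figure is a claim about holding time, so the storage actually ordered has no stated support even when the steps are read in sequence. The numbered procedure also describes only patients diagnosed with acne and never says when or how control blood is drawn and held. Equal handling is therefore inferred from the general wording of step 6c. A sentence and a log line per specimen would cost little, and handling times that are not logged at collection may be impossible to recover later. Participants are also told that they will learn their own zinc level.

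The first point stands: the refrigerated stage is undocumented, and the wording of steps 6a to 6c does not fit together. The silence on control specimens also stands, but silence is not evidence of different handling. The logging proposal is good practice, but it is not needed to resolve the wording, and its value depends on a storage effect that the document gives no reason to expect. The laboratory's terms may lie in the memorandum cited in step 6b. Since that is not available here, the basis for refrigeration is unknown rather than shown to be absent.

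**Conclusion.** The inconsistency is genuine but minor, and it does not call for a change to the plan. Storage before pick-up falls outside the only stated stability condition, yet the document gives no reason to think that this alters total zinc measured after ashing, and no sign that handling differs by group. Following the procedure as written is not shown to give a wrong or less reliable comparison. The investigator and laboratory can close the gap from the laboratory's own specimen-storage limits, with one condition for all specimens.

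No size can be put on any effect on zinc itself. Random handling error at 10% to 25% of the within-group SD would cost about 0.3 to 1.7 points of power, and at 50% about 7 points, all on assumed values.

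The conclusion assumes that the refrigerator runs below 15 °C, that specimens are mixed and digested whole, and that step 6c is applied alike to cases and controls. Evidence that cooling changes the assay result, or that controls were stored differently, would reopen the question.
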